9.9 Protocol Deviations

There will be no protocol deviations, because the surgery will be performed after a standardized procedure for each patient at the beginning of the trial and the follow-up visits will be performed after a predefined standardized protocol. There are no treatments planned after surgery. The tight follow-up plan will secure patient safety.

10 GENERAL CONSIDERATIONS: REGULATORY, ETHICAL, AND TRIAL OVERSIGHT

10.1 Regulatory and Ethical Considerations

The Investigator is also the sponsor. He is responsible for compliance with the below laws and regulations. The clinical trial will be conducted in compliance with the protocol, with the regulation and with the principles of good clinical practice according to Annex I section D 17 (a) CTR 536/2014, the declaration of Helsinki, the Council for International Organisations of Medical Sciences (CIOMS) International Ethical Guidelines, ICH Good Clinical Practice (GCP) Guidelines (the investigator holds the ICH-GCP-certificate). Additionally the German Bundesdatenschutzgesetz (BDSG) and the General Data protection Regulation (regulation (EU)2016/679), GDPR will be followed.

The study will only start after a positive ethic vote is obtained.

The benefit-risk balance is in focus of the trial and will be evaluated when safety issues occur. The efficacy of the procedure is also in focus and only when the efficacy is over 80% the ethical balance is given.

10.2 Committees

This is an investigator-initiated trial (Investigator=Sponsor). There will be no committee be involved in the trial.

10.3 Informed Consent Process

The informed consent process starts with the first appointment. When patients are referred for partial meniscal replacement, they will be informed about the clinical trial. If the patient qualifies for participation in the study based on the inclusion and exclusion criteria, the investigator will explain the treatment procedure for partial meniscus replacement with Spongioflex® and the planned investigator-initiated trial (planned visits, data protection, etc.). Patients also receive an information sheet explaining the study and the surgical procedure, the advantages and disadvantages, the risks, and the follow-up treatment. The information sheet also provides information about the planned investigator-initiated study (planned visits, data protection, etc.). After a sufficient reflection period, the patient must sign the declaration of consent to participate in the investigator-initiated study and the data protection declaration. Without these written consents, the patient cannot be included in the investigator-initiated trial. After the signatures have been obtained, the patient is included in the investigator-initiated trial. The patient decides whether to undergo surgery. The operation is performed in accordance with standard clinical practice and the usual risk information for the surgical procedure. This is done using the standard information sheet used in the respective hospital. In this, patients are usually informed about the procedure, the treatment alternatives, the risks, and the follow-up treatment. Enrollment in the trial does NOT occur during an emergency in which the participant or their legally authorised representative is not able or available to give consent.

Rescreening

Rescreening can be performed when the patient did not meet the inclusion criteria (e.g. age) in the first attempt. If any exclusion criteria are not any more valid (e.g. BMI) rescreening can be performed. The screening will be performed even, when the patient does not agree to participate in the study, because then the patient will be treated/or not, but the data will not be collected for the study. The informed consent will be obtained after enrollment, when inclusion criteria are met and no exclusion criteria are met. Screen failure will be left in because the study model is full analysis set. When re-screening is performed informed consent is mandatory for participation in the study.

There will be no collection of (biological) samples in the study.

10.4 Data Protection

All collected and stored data of the study participants are treated confidentially and are subject to medical confidentiality. The patient's right to respect his/her privacy and the protection of data concerning him/her is guaranteed in accordance with the General Data Protection Regulation (DSGVO) of 25.5.2018. The personal data are only accessible to the performing physician in the study center, who has included the patient, or to employees commissioned by him. The personal data will only be processed in pseudonymous form. For this purpose, the study center creates a pseudonymization list, which is only known to the authorized employees of the study center. The data are pseudonymized in ascending order for scientific analysis, so that third parties (biometrists) cannot establish a personal reference. In this study, the investigator and the sponsor are the same person. Therefore, no transfer of data between the investigator and the sponsor is necessary. Furthermore, it is intended that the investigator performs the analysis himself. If a biometrist (statistician) must be consulted for the evaluation, he will only receive the pseudonymized CRF, from which no conclusions can be drawn about the patient or the clinic in which the patient was treated. The pseudonymization will be performed by attributing numbers and special characters. Initials and birth dates are not used for pseudonymization and are omitted. For the patient, there is a right of access and objection at any time with the possibility to delete all collected data. Patients can withdraw their consent to participate in the study and to data collection at any time without giving reasons. This does not change medical treatment. The study is therefore a minimal interventional study, as the treatment is conducted in the same way with and without study participation. The only difference is that the data are only stored in the patient chart if the patient does not participate in the study and not transferred to the CRF after pseudonymization. If the patient's consent is withdrawn, the responsible bodies will immediately check the extent to which the stored data are still required. Data that are no longer required will be deleted immediately, unless statutory documentation and reporting obligations prevent this. However, the data processing conducted up to the point of withdrawal remains lawful.

Safety of Data and patients is monitored by a CRA (clinical monitor).

In case of a data security breach the patient will be informed about the breach without undue delay and at the latest within 7 days. Additionally, the data security breach will be reported to the EU portal and EU database (via the CTIS) without undue delay and at the latest within 7 days. The template provided at the CTIS should be filled in and all information which are described under 5 and appendix IIIb of the Guideline for the notification of serious breaches of Regulation (EU) No 536/2014 or the clinical trial protocol (EMA/698382/2021) from the 30th of June 2023.

10.5 Early Site Closure or Trial Termination

Site closure:

The Investigator and the Sponsor are the same person. The investigator has the right to close the site. This could be for physical or financial reasons. The ethic committee will be informed and a prompt notification of the patients will be performed. The treatment is the surgery and is terminated when the site is closed. The remaining follow-up's will be performed by an orthopedic surgeon, who is familiar with the procedure and the follow-up.

Termination or suspension:

The investigator-initiated trial may only be terminated prematurely for ethically relevant, i.e., medical/scientific reasons.

Premature exclusion of a patient from the study:

- If, during the waiting period for the Spongioflex® graft, changes in the patient's state of health occur that constitute a contraindication for partial meniscal implantation (e.g., infection of the knee joint, tibial

plateau fracture), the physician conducting the study must withdraw the patient from the investigator-initiated trial if this appears reasonable and necessary for medical reasons.

Premature termination of the entire study: Reasons for premature termination of the investigator-initiated trial include:

- If the identifiable risks outweigh the expected benefits.
- If an unreasonable risk to patients is apparent
- If unexpected serious adverse events (SAE); Suspected Adverse Drug Reaction (SADR) occur that are causally related to the insertion of the meniscal implant they will be reported to the EudraVigilance database. A new benefit/risk balance evaluation is performed and after the analysis it is decided if the study will be continued. Patients will be followed up until the SAE or SADR is solved, if necessary, in the hospital, otherwise as outpatient.
- IF SUSARs are reported, a new benefit/risk balance evaluation is performed and after the analysis it is decided if the study will be continued.

If the investigator-initiated trial is terminated or suspended prematurely, the study director will inform the regulatory authority(ies) of the termination or suspension and provide a statement to that effect. The Ethic Committee will be promptly notified and provided with a detailed written explanation for the study director's termination or suspension of the investigator-initiated trial, as specified in the applicable regulatory requirements. If the investigator-initiated trial is terminated or suspended prematurely for any reason, study participants will be notified immediately.

- In the event of premature termination or suspension of the investigator-initiated trial, further follow-up of patients will continue according to standard clinical practice

Patients can stop the participation of the study at any time, without giving the reason for it.

11 GENERAL CONSIDERATIONS: RISK MANAGEMENT AND QUALITY ASSURANCE

11.1 Quality Tolerance Limits

Quality tolerance limits are defined in the inclusion/exclusion criteria. The main criteria which may lead to exclusion of the patient from the trial are age (must be over 18 years and under 60 years) and BMI (must be $<30 \text{ kg/m}^2$). The investigator expects a 20% drop in total. If the drop-out will be higher, this could significantly impact the study results. Protocol deviations and violations will not occur, because the surgery is performed after a standardized procedure. The patient does not have any impact on this procedure.

The percentage of withdrawal will be small, because the burden of the trial is very low (filling the 3 questionnaires at the follow-up-visit). The investigator predicts a maximum of 5 % withdrawal, which is included in the 20% mentioned above.

Incomplete data will occur due to lost to follow-up, withdrawal or due to progression of osteoarthritis up to TKA. Progression of osteoarthritis is a very slow process; thus a 2.5% possibility would be defined by the investigator for incomplete data related to progression of osteoarthritis up to TK.

AE and SAE occur at any time and may be not related to the IMP used. SAE not related to the investigational product do not impact study results. SADR/SUSAR's do impact study results. Because human allogeneic cortical bone (in any supply form) was transplanted in different forms several thousand-fold, the manufacturer (DIZG gGmbH, Berlin, Germany) did not receive any information about and SADR or SUSAR up to now.

The IMP is not a pharmacological drug and the administration is not over the trial period. The IMP will be implanted during surgery and remains in the body. It has no systemic effect and it is not a medical device.

Patient follow-up will be the same for patients included in the trial or not, thus the lost to follow-up will be below 10 %, because the follow-up-visits are only a minimal burden.

For ethical reasons, there is no randomization in the trial. The patient decides, if he will be operated, or not. Even if the patient will decide not to be operated in the first round, they have the possibility to change to the surgery group at any time. Thus, there is no pressure on the patient and there is no incorrectly randomized patient.

All this Quality tolerance limits are monitored during the trial via a clinical monitor (CRA).

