3 TRIAL OBJECTIVES, ENDPOINTS AND ESTIMANDS

3.1 Primary Objective + Associated Endpoint and Estimand

| Primary Objective | Primary Endpoint |
|---------------------------------------|--|
| To evaluate efficacy of the procedure | Improvement of PROMs (KOOS, IKDC, VAS Pain Score) 2 and 5 years after surgery compared to scores of the non-operated group and compared to pre-surgery scores. |

Primary Estimand (Variable): Difference in PROMs after 2 and 5 years

Endpoint: 2 and 5 years after surgery/enrollment, or progression to TKA

Treatment: varies with the group chosen by the patient (operated or not operated)

Population: male and female patients between 18 and 60 years

Intercurrent event: progression of osteoarthritis up to TKA, lost to follow up, premature death, the patient wishes to change to the operated group after a certain time (The process: progression of osteoarthritis is very slow. It will be very unlikely that more than 1 patient wants to change to the operated group within the 5 years of the trial. The same is true for progression to TKA. The possibility to change later in the operated group will take off the pressure from the patient to make the “wrong” decision now.)

Population-level summary: The primary objective is to compare the PROM change from baseline between the operated and non-operated group after 2 and 5 years. The difference in obtained PROMS will be evaluated.

Estimand Description: The Estimand are the Difference in PROMs. This includes specific knee scores (IKDC, KOOS) and the VAS-Pain Score. IKDC and KOOS have values between 0 and 100 and the higher they are as better the function of the knee. The VAS Pain Score has values between 0 and 10 and the higher the score the higher the pain.

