4 TRIAL DESIGN

4.1 Description of Trial Design

Description of Intervention Model

This investigator initiated; low intervention trial is performed with 2 groups. The intervention group is the group of patients who will be operated. The control group are the patients not willing to be operated. Due to the incidence of patients with partial meniscal loss in the last years in the private praxis of the principal investigator 30 patients in the operated group and 10 patients in the non-operated group will be recruited within 2 years of recruitment. The study will be performed to prove patient safety and efficacy of the procedure. The process of progression of osteoarthritis is very slow. It will be very unlikely that more than 1 patient will be in this situation and wants to change to the operated group within the 5 years of the trial. The same is true for progression to TKA. The possibility to change later in the operated group will take off the pressure from the patient to make the “wrong” decision now.

Description of Trial Duration

The total trial duration will be 7 years. The recruitment period will be 2 years. Follow-up is 5 years. Depending on, if the patient will be operated or not, the time until surgery will add on these 5 years. The substance used (human cancellous bone) does not have a dose. It will be used in various dimensions.

Method of Assignment to Trial Intervention

This is a single centre trial. The initiator of the trial will perform the trial on its own. Due to the small number of patients included, the investigator will perform all visits on its own. There is no randomization. The patient decides if he/she will be operated or not. There is no blinding. A clinical monitor will perform data monitoring. There are no plans for a data monitoring committee due to the small number of patients and small number of data recorded. Bias is minimized by investigating the MRI images after a standardized protocol. The PROMs are filled in by the patient without the help of the investigator. The analysis will be performed by the investigator using statistical software. Patients from the non-operated group can transition to the operated group at any time. There are no rules for transition.

An interim analysis is planned after 2 years. See details in section 9.7

There will be no sample collection during the trial. In the moment there is no extension of the trial over the 5 years planned.

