7.3 Lost to Follow-Up

This is an orthopedic trial. The surgery is the start point and after the surgery there are no treatments. There are only follow-up visits, which include an MRI and 3 questionnaires (IKDC, KOOS, CRF). Follow-up-visits are at the end of the hospital stay, 6 weeks after surgery (both for operated patients only), and then for all patients: after 6, 12 and 24 months and after 5 years.

Lost to follow-up will occur because the trial population are mainly young active people. They will move for work or private reasons and may not finish the visits. In the number of patients for the trial lost to follow-up is included in the statistical calculations. The investigator will explain, when the informed consent is discussed with the patient, the importance of attending the follow-up-visits. If the investigator has the impression that the patient will not be compliant regarding the follow-up-visits, he will not include the patient in the trial.

When a patient is lost to follow up, the data up to the last visit attended will be used.

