9 STATISTICAL CONSIDERATIONS

Data analysis complies with ICH E9 Guideline and ICH E9(R1) Guideline. This clinical trial is to confirm patient safety and efficiency of the procedure.

For this reason, as primary objective PROMs (IKDC, KOOS and VAS-pain score) will be evaluated before surgery/at the beginning of the trial and then starting at 6 months after surgery/beginning of the trial for the operated or non-operated group, respectively. The evaluation will be performed also after 12 and 24 months and after 5 years. A primary analysis will be performed 2 years after surgery/start of the trial.

At the beginning of the trial and prior to operation demographic and baseline data will be collected and summarized for both groups.

For safety, there will be an evaluation of complications, AE, SAE and SUSARs at each follow-up visit (at the end of the hospital stay, after 6 weeks, after 6, 12, 24, months and after 5 years, for the operated group). The number of AE, SAE and SUSARs will be recorded and evaluated at each visit. MRI evaluation starts at the follow-up visit 6 weeks after surgery for the operated group and 24 months after the start of the trial for the non-operated group. The evaluation of the MRI will be performed after a modified graduation of Genovese et al. [32]. Additionally, there will be the meniscal size evaluated and if there is an extrusion of the meniscus and how big the extrusion is. There will be a Kaplan-Meier-time to event curve for both groups regarding progression of osteoarthritis up to TKA. The analysis will be conducted on all participant data after 2 years and after 5 years.

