9.3 Analysis Supporting Secondary Objective(s)

Secondary objectives are:

Safety of the patient, efficacy of the procedure, MRI image description and patient satisfaction.

Patient safety will be analyzing the number of AE, SAE and SUSARs and will be compared for both groups. The numbers obtained will be compared in a Chi-Square test. SUSARs will only occur, if any, in the operated group and thus cannot be compared to any other value. For categorial variables. Efficacy of the procedure will be analyzed by counting the number of failed procedures in the operated group. Because this value will only be determined in the operated group, there is no statistical analysis. The efficacy of the procedure must be over 80%. If the failed procedures are higher than 20 % the benefit-risk balance will be re-evaluated. The MRI signal will be evaluated after a modified scheme of Genovese [32]. The size of the meniscus and the amount of extrusion of the meniscus will be measured and recorded in both groups. The obtained numbers will be compared to the other group at the same time point and to the value before surgery/at the beginning of the trial. This will be performed with an unpaired t-Test if the values are normally distributed or with the Mann-Whitney-U-test for not normally distributed values. Patient satisfaction is a categorial value and will be only evaluated in the operated group. The number of patients who are very pleased, pleased, not pleased, very unsatisfied will be described by means of frequency tables and plots.

Intercurrent event are: progression of osteoarthritis up to TKA, lost to follow-up, premature death, the patient wishes to change to the operated group after a certain time. If these events happen, the data will be available until the event. Last date recorded will be analyzed. Progression of osteoarthritis up to TKA will be recorded as fail and will be reported as this. Patients changing to the operated group will be analyzed up to the date of change in the non-operated group. Missing data will not be estimated. A drop-out rate (lost to follow-up, premature death) of 20% is expected and accepted.

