9.7 Interim Analyses

Interim analysis will be performed 2 years after surgery/start of the trial. After knee surgery, the usual follow up is 2 years. Because long term results are important for the efficacy of the procedure, evaluations will be performed also after 5 years. The analysis will be performed by the investigator. The statistical methods used are described under 9.2 and 9.3. The outcome data will be seen only by the investigator while the trial is ongoing. The 2-years result will be published in an international orthopedic journal. There will be no group sequential test and no spending function. The number of patients is fixed at 30 in the operated group and at 10 in the non-operated group. There will be no enrollment until an event occurs. There will be no trial adaptation or changes to the eligibility criteria.

Stopping criteria are: If AE, SAE and SUSARs change the benefit-risk balance, there will be a new benefit-risk balance evaluation and after this evaluation it will be decided if the trial will be stopped. The investigator expects a maximal 20% failure rate of the procedure. If the failure rate is higher a new benefit-risk balance evaluation must be performed and after the evaluation it must be decided if the trial continues. If the safety of the patients is not any more given, the trial should be stopped.

The investigator also has the right to stop the trial. This could be because of the closure of the site. See 10.5 for details.

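### The routine-care argument for loss below 10% does not cover the 5-year primary time point or the controls, and self-completed PROMs are tied to clinic visits

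*Protocol*

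**What the plan says.** **Loss forecast.** Section 11.1 states: "Patient follow-up will be the same for patients included in the trial or not, thus the lost to follow-up will be below 10" per cent. It adds a second reason in the same sentence, the low burden of the visits. It also expects 20% drop-out in total, of which at most 5% is withdrawal, and 2.5% incomplete data because of progression to TKA.

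**Usual care.** Section 9.7 states: "After knee surgery, the usual follow up is 2 years". It then says that, because long-term results matter, "evaluations will be performed also after 5 years". Section 2.2 describes filling in the questionnaires at the planned visits as specific to the study.

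**Primary time points.** Section 3.1 defines the primary endpoint as "Improvement of PROMs (KOOS, IKDC, VAS Pain Score) 2 and 5 years after surgery", and both hypotheses in 9.2.1 name 2 and 5 years. Section 9 also says: "A primary analysis will be performed 2 years after surgery/start of the trial".

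**How PROMs are collected.** Section 4.1 states: "The PROMs are filled in by the patient without the help of the investigator". Sections 8.11 and 11.1 place completion at the follow-up visit. Under 7.1.2, a patient who cannot use a visit window waits for the next one. On the cause of loss, 7.3 says of its young, active patients: "They will move for work or private reasons and may not finish the visits". Section 9.2.3 makes no assumptions for missing data and analyses the last observation.

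**The 20% elsewhere.** Section 9.3 states: "A drop-out rate (lost to follow-up, premature death) of 20% is expected and accepted". Sections 6.7 and 9.8 also use 20%, each with a different scope.

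**The concern.** A forecast of low loss is only as good as its reason. If patients would return to the practice anyway, low loss is plausible. If the visit exists only because of the trial, that reason is gone. The 5-year visit is of the second kind by the protocol's own account, and it is half of the primary endpoint. The 2-year norm in 9.7 is stated for knees that have been operated on, so it says nothing about the control group at any visit.

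The collection rule adds to this. The primary outcome is a set of questionnaires that the patient answers alone, yet the protocol obtains them only from patients who come to the clinic. The cause of loss it names is moving away, which prevents attendance but does not by itself prevent answering a form. At stake are missing or outdated primary data at 2 and 5 years in a non-randomised, unadjusted comparison with 10 controls.

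**Working it through.** **1. The plan's own calculation with a loss rate (9.8).** The below-10% figure has no calculation behind it. The only one that uses a loss rate is the sample size.

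- Inputs: 30 operated and 10 non-operated, effect size 2.0, two-sided unpaired t-test (9.2.1), 20% loss.
- Remaining: 30 × 0.8 = 24 and 10 × 0.8 = 8.
- Noncentrality = d × √(n1·n2/(n1+n2)) = 2.0 × √(24·8/32) = 2.0 × √6 = 4.90, with 30 degrees of freedom.
- Power at alpha 0.014: 0.9857, against 0.985 stated.
- For 30/10 at alpha 0.00655: 0.9935, against 0.993 stated.

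Both reproduce. The calculation uses 20%, so the below-10% figure drives no number in the plan.

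**2. Is below 10% compatible with 20% in total?** Adding the components in 11.1: below 10% + at most 5% withdrawal + 2.5% TKA = below 17.5%, which is less than 20%. There is no arithmetic conflict.

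**3. Is the 20% one quantity?**

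| Section | What the 20% covers |
|---|---|
| 6.7 | loss to follow-up or withdrawal of consent |
| 9.3 | loss to follow-up and premature death |
| 9.8 | loss to follow-up alone |
| 11.1 | total drop-out, including withdrawal |

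These are four scopes for one percentage, equal to 8 of 40 patients in each case.

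**4. Does the routine-care premise reach each primary time point?**

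| Group | 2 years | 5 years |
|---|---|---|
| Operated | attendance yes (9.7); questionnaires study-specific (2.2) | no, added by the trial (9.7) |
| Non-operated | no norm stated | no norm stated |

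**5. How long does a patient wait after a missed slot (7.1.2)?** U5 is at 24 ± 1 months and U6 at 60 ± 3 months.

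- Shortest gap: (60 − 3) − (24 + 1) = 57 − 25 = 32 months.
- Longest gap: (60 + 3) − (24 − 1) = 63 − 23 = 40 months.
- After U6 there is no later slot.

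**6. What value is analysed?** Under 9.2.3, a patient last seen at U5 would have a 2-year score standing for year 5, or no 5-year score, depending on how the rule is read. A patient last seen at U4 would have a 12-month score, or none, at 2 years. Each control concerned is 1 of 10.

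**7. Does power suffer?** At effect size 2.0 and two-sided 0.05, under assumed loss rates spread evenly over the groups:

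| Loss | Operated/non-operated | Power |
|---|---|---|
| 10% | 27/9 | 0.999 |
| 20% | 24/8 | 0.997 |
| 50% | 15/5 | 0.955 |

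In the extreme case where all 8 losses are controls (30/2), power is 0.755. At the planned effect size, the issue is the quality of the 5-year data rather than power.

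**The case against.** The case for leaving the text alone has real force.

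- The below-10% figure has a second reason, low visit burden, and 7.3 adds measures: attendance is stressed at consent, and patients thought unlikely to return are not enrolled. This stands, but neither reason answers relocation, which 7.3 still expects.
- Section 9 places a primary analysis at 2 years, where 9.7 supports routine attendance for operated patients. This stands and confines the contradiction to year 5 and the control group.
- The 24-month and 5-year visits include MRI in both groups (7.1.1), physical examination (8.3.1) and adverse event collection (8.4.2), so attendance has a purpose. This stands, but the primary PROMs do not depend on those procedures.

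A reader might also infer more than the text allows:

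- *That 11.1 and 9.3 contradict each other on the same quantity.* They do not. The 20% in 9.3 includes death, and below 10% is one component within the total in 11.1.
- *That the trial is underpowered because of the optimistic forecast.* The sample size allows 20% and reproduces.
- *That patients will be lost needlessly, or that exactly those who could have answered will be lost.* The protocol describes completion at the visit but does not forbid another route. It does not say that every loss is a move or that those who move stay reachable.
- *That remote forms would recover a stated share of losses.* The documents give no basis for one, and withdrawals and deaths could not be recovered this way.

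**Conclusion.** The point holds in a limited form. The routine-care reason in 11.1 does not extend to the 5-year primary time point (9.7, 2.2), nor to the non-operated group. This leaves the forecast for that visit resting on low burden alone. The 20% has four scopes and needs one.

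The collection rule is the more practical weakness. Self-completed primary outcomes are tied to attendance, a missed U5 waits 32 to 40 months for the next slot, a missed U6 has none, and the last observation is then analysed. A patient who moves may therefore supply a stale value or none at 2 or 5 years, and among controls each such patient is one tenth of the group.

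This does not undermine the stated power. Its size in patients cannot be estimated from the documents, because they give no 5-year loss rate and no share of losses due to relocation. The conclusion assumes that 8.11 and 11.1 describe the only collection route, since no section provides another. It is a cheap and worthwhile improvement, not a fatal flaw.

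**What to change.** - **Sections 7.1.2 and 7.3:** state that a patient who cannot attend U3, U4, U5 or U6 completes KOOS, IKDC and VAS pain by post or electronic form within the same visit window. Record the mode of completion. Do not count the patient as lost for the primary endpoint. MRI and examination remain missing for that visit and are reported as such.
- **Section 11.1:** drop the argument from identical follow-up for year 5, and do not apply it to the non-operated group. If a loss figure is kept, give its basis separately for 2 and 5 years.
- **Sections 6.7, 9.3, 9.8 and 11.1:** use one definition of the 20%, stating whether it includes withdrawal, death and progression to TKA.

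The cost is postage or an online form and a few sentences of protocol text. A small difference between modes of completion is possible, and recording the mode allows it to be examined.
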